MUSE Device to Improve Sleep Quality in Midlife Women

NCT05972486

31January2024

IRB Minimal Risk Protocol Template

General Study Information

Principal Investigator: [name], PA-C

Co- Principal Investigator: [name], DNP

Co- Investigator: [name]

Lead Coordinator: [name]

Study Title: MUSE Device to Improve Sleep Quality in Midlife Women

Protocol version number and date: V4 01/31/2024

Research Question and Aims

Hypothesis:

We hypothesize that the daily use of the Muse-S headband system will be an effective strategy for improving the sleep quality in peri- and postmenopausal women. We anticipate that the women who utilize the Muse-S headband will have improvements in time to sleep onset and sleep maintenance. We also anticipate a positive correlation between duration and frequency of use of the device and the improvement in sleep quality.

Aims, purpose, or objectives:

1. To obtain preliminary evidence regarding the feasibility of using the Muse-S headband system for management of sleep disturbances in peri- and postmenopausal women.
2. To obtain preliminary data on the effectiveness of the Muse-S headband system for management of sleep disturbances in peri- and postmenopausal women and to ascertain whether duration of treatment impacts efficacy.
3. To obtain preliminary data on the effectiveness of the Muse-S headband system in improving secondary outcomes of sleep quality including stress levels, mood and sexual function.

The overarching purpose of this study is to obtain preliminary evidence regarding the efficacy of the Muse-S headband system for management of sleep disturbances (insomnia and sleep disruption) in midlife women. This goal will be achieved with the following specific aims:

Objectives: The overarching goal of this project is to test the feasibility and efficacy of the Muse-S™ Headband, an electroencephalographic device, in management of sleep disturbances in midlife women.

Background:

Sleep problems (insomnia and sleep disruption) affect nearly half the women during the menopause transition and the postmenopausal years. The etiology of sleep disturbances in peri- and postmenopausal women is

multifactorial, resulting from a combination of the direct effect of decline in estrogen level, vasomotor symptoms, mood changes, and chronic pain, among others. It is estimated that there will be 90 million postmenopausal women in the US by the year 2060. Therefore, untreated menopause-related symptoms, including sleep disturbances, have the potential to be a significant public health problem. Unlike several other symptoms of menopause, sleep disturbances often do not improve as the women get farther into menopause. Chronic sleep disturbances have multiple adverse health consequences including negative impact on mood, cognition, work performance, sexual function, and the overall quality of life. There is fairly strong evidence linking chronic sleep disturbance with weight gain and obesity in midlife women. Finally, sleep disturbances are also associated with increased risk for cardiovascular disease (CVD), including greater odds of hypertension, coronary artery disease, and stroke. Given that CVD is the number one killer of postmenopausal women, the importance of managing CVD risk factors cannot be overemphasized in this patient population.

Although prescription therapies such as menopausal hormone therapy, antidepressants, and hypnotics are effective in treating menopause-related sleep disruption and chronic insomnia, many patients avoid their use due to concerns regarding adverse effects, contraindications, or personal preference. The potential for increased breast cancer risk with extended hormone therapy use has caused a dramatic decline in the rates of hormone therapy use. As such, menopausal hormone therapy is not indicated for management of isolated sleep disruption (in the absence of significant vasomotor symptoms) in midlife women. There are concerns regarding side-effects and long-term toxicity even with the non-hormone prescription medications, particularly with chronic use, which is often needed in this condition. Not surprisingly, women frequently have reservations about using medications to manage sleep on a long-term basis. Therefore, investigating non-prescription therapies for management of this common condition in midlife women is of utmost importance.

Behavioral interventions, specifically cognitive behavioral therapy, exercise, and mindfulness/relaxation have been shown to be safe and reasonably effective for management of insomnia and sleep disruption in midlife women. These are typically the first line interventions for management of sleep problems in midlife women. However, the evidence supporting the use of these interventions in midlife women is somewhat weak with a need for further research identified by the experts. Moreover, some of these interventions can be difficult to access, limiting their use. Women can also find it hard to engage in meditation. There is a need to study novel behavioral interventions for management of sleep disruption in midlife women that overcome some of the barriers with the existing treatment modalities. The Muse-S™ headband offers an opportunity to fill this gap by giving patients real time biofeedback with electroencephalogram (EEG) technology to guide them and build confidence in their abilities to incorporate meditation in their daily habits. Once calibrated to an individual, the Muse-S headband distinguishes between active and calm brain states to provide real time performance feedback. This is achieved by converting EEG signals, measured over the frontal and temporal cerebral cortices, into measures of the state of the brain (active versus calm). This biofeedback allows for real time reinforcement of successful meditation. Additionally, the device is portable and easily accessible to the public making it a viable behavioral therapy intervention for patients. The Muse-S headband is being used in studies in the division of General Internal Medicine on patients after breast cancer surgery, those with pain-related to fibromyalgia, and in healthcare providers who are experiencing stress.

The proposed study will assess the impact of the Muse-S headband on the sleep quality in peri-and postmenopausal women experiencing subjective sleep disturbances. The study will also evaluate the impact of the Muse-S headband on the secondary outcomes of mood, quality of life, stress, and sexual function. These

parameters are often negatively affected by poor sleep, and therefore improvement in sleep quality is likely to impact mood, anxiety, quality of life, stress and sexual function favorably.

Study Design and Methods

Methods:

All study participants will receive a new Muse-S headband system at study entry and will be asked to utilize it daily for a minimum of 10 minutes day for a period of 6 months (24 weeks). Three of the seven sessions per week will specifically be asked to be mind meditation.

The participants will be provided instructions on setting up the device and connecting it to their smart device. They will also receive general education on the different features of the Muse-S Headband. They will have access to specific education on meditation. They will also have access to sleep tools on their app.

The participants will complete the ASCQ-Me Sleep Impact-Short Form, Epworth Sleepiness Scale and Sleep Quality Assessment PSQI for evaluation of their sleep. In addition they will also completed the the Patient Health Questionnaire (PHQ-9), Generalized Anxiety Disorder Scale (GAD-7), Female Sexual Function Index (FSFI) and Female Sexual Distress Scale (FSDS-R), Quality of Life- (LASA), Perceived Stress Scale (PSS) and Resilience- (CD-RS10). Quality of Life, mood, anxiety, stress and sexual function are often negatively impacted by poor sleep.

The weight, body mass index and blood pressure will be obtained from the MWSHC, Community Internal Medicine, Executive Health, or Family Medicine visit data at 0 and 6 months.

The data will be recorded in REDCap at baseline, 3 months, and 6 months.

All study participants will have access to The Muse-S™ Headband system's customer service team based in Toronto, Canada, by telephone and email for assistance should they experience technical problems with the device.

Server Data: As the subject completes any Muse-S sessions, the information from these sessions will be uploaded to the Muse-S ICloud servers hosted by Google. Each subject will be able to see their own data at the end of each session, and data from the previous session stored in the "me" tab in the app. Subject to the study organizers ensuring that the subjects have signed the appropriate consents, study organizers will have access to each subject's data to monitor compliance, performance and outcomes, but will not get access to Journal entry information (if subject chooses to write a Journal entry). These data that the study organizers will have access to may include the study-specific identification number, gender, and age of the subject, the session type, the time and duration of each session, EEG data, heart rate (PPG) data, and the performance per session. Interaxon's privacy policy, which can be found at

██████████ will apply to Interaxon's use of the subjects' data. To maximize protection of the individual's privacy, the study organizers will ensure that the subjects are assigned anonymized email address and names for use in the Muse -SÔ application and when contacting the Muse-SÔ customer support. To ensure that no health data is shared with Interaxon, the study organizers have agreed to ensure that no health data will be shared with Interaxon. At the end of the study, the data collected in Google ICloud Server associated with study email addresses will be deleted.

Subject Retention

Participants will not be remunerated for participating in this study, but they will be allowed to keep the Muse-S headbands.

Study Design

We will use standardized procedures to ensure uniform instructions and support for all subjects for the recruitment, screening, and study entry.

Recruitment:

Women that come to the Menopause and Women's Sexual Health Clinic (MWSHC), Community Internal Medicine, Executive Health or Family Medicine at Mayo Clinic Rochester, who are identified as having significant sleep disturbance based on a standard questionnaire used for assessment of sleep quality and duration- the Pittsburgh Sleep Quality Index (PSQI) score >5 are recruited to the study based on the inclusion/exclusion criteria. If the participant is interested in the study the clinician will notify the study coordinator of participants eligibility, study coordinator at that time will set up a designated time to sign consent and get the participant enrolled in the study.

Participants will not be reimbursed for their time spent in the study, but all participants will be given the option of keeping the Muse-S™ Headband system for continued use post study participation.

Consent and Screening:

Study coordinator will meet with the potential participant who has expressed an interest in participating in the study. They will begin by introducing the study details, and after determining that the subject has continued interest in study participation, will move on to the study consent. If the subject chooses to consent, they will screen the participant for study entry inclusion/exclusion criteria. If the study entry criteria are met, the subject will begin their study participation. They will be asked to complete the study questionnaires.

Please note: Participants must have access to an iOS or Android capable device to take part in this study in order to interact with the Muse-S™ Headband system.

Treatment phase:

During the first three months of study, participants will be asked to complete the intervention portion of the study using the Muse-S™ headband. If the MUSE device is not being used at least 3x a week for 10 minutes a day, the participant may get a reminder email or a phone call to remind them to use the Muse-S™ headband

system. Participants will receive an email link at 90 days from REDCap to complete their questionnaires for the study. If not completed in a timely manner there will be reminders by email and/or phone to complete.

Study Follow-Up Visit:

The study will consist of follow up at 3 month and 6 months.

3 month (questionnaire only visit): questionnaires will be sent via email **NOTE:** once questionnaires are complete the study coordinator will check the PHQ 9 score the same day the participant completes the questionnaire via the electronic link. The coordinator will immediately notify the investigators if the score is severe or subject indicates suicidal ideation. The investigators will contact the patient immediately (same day) and if there is concern for active suicidal thoughts, they will recommend the patient pursue emergency evaluation (such as local ED or 988 suicide prevention hotline) or contact local authorities for a welfare check if the patient declines. If severely depressed but no active thoughts of self-harm/plan, we will recommend an appointment with their PCP, EAP (if Mayo Employee) and offer the resource Psychology Today to help find a mental health provider.

6-month (on-site visit /phone visit): Consists of a study coordinator visit at Menopause and Women's Sexual Health Center for a final weight, body mass index, blood pressure check and questionnaires for local participants. Participants that are not local or cannot make an on-site visit, questionnaires will be sent by email to be completed and a phone visit will be scheduled with study coordinator. **NOTE:** The PHQ 9 questionnaire will be reviewed at the time of the visit. If the score is severe (20-27) or the subject indicates suicidal ideation the investigators ([name] and [name]) will be notified and will discuss with the patient. If concern for active suicidal thoughts, the investigator will initiate immediate emergency evaluation. If severely depressed but no active thoughts of self-harm/plan, we will recommend an appointment with their PCP, EAP (if Mayo Employee) and offer the resource Psychology Today to help find a mental health provider.

Subject Information

Target accrual: 50 women

Subject population (adults):

This will be an open label single-arm clinical trial that will recruit **50 peri- and postmenopausal women** from the Menopause and Women's Sexual Health Clinic (MWSHC), Community Internal Medicine, Executive Health, or Family Medicine at Mayo Clinic, Rochester, who are identified as having significant sleep disturbance based on a standard questionnaire used for assessment of sleep quality and duration- the Pittsburgh Sleep Quality Index (PSQI). The PSQI is a 19-item questionnaire making up 7 clinically derived component scores. Each of the 7 clinically derived components is given a score from 0-3 to obtain a total score ranging from 0-21. Higher scores indicate worse sleep quality, with a **PSQI score >5 indicating poor sleep quality**.

Inclusion Criteria:

- Women between the ages of **45-65 years** (women in the menopause transition or in menopause, based on clinical assessment)
- **PSQI score >5**, with overall sleep quality rating of "fairly bad" or "very bad".

- Motivation VAS score equal to or greater than 5 with overall motivation rating of on a scale of 0-10 with 0 being not motivated at all and 10 being extremely motivated
- Access to an iPad, iPhone, or android device
- Have ability to provide informed consent

Exclusion Criteria:

- Suspected or untreated obstructive sleep apnea
- Moderate to severe vasomotor symptoms warranting prescription medication use. The FDA categories for hot flash severity are classified as mild (sensation of heat without sweating), moderate (sensation of heat with sweating, able to continue activity), or severe (sensation of heat with sweating cause cessation of activity).
- Use of hormone therapy or hypnotic agents
- Use of supplements known to affect sleep
- A known, active, untreated clinically significant psychiatric condition
- Use of an investigational drug within 30 days of study enrollment or presence of a known history of any condition or factor judged by the investigator to preclude participation in the study or which might hinder adherence.
- Currently (within the past 3 weeks) been practicing mindfulness training on a weekly/regular basis

Potentially eligible participants will be identified from the MWSHC, Community Internal Medicine, Executive Health, or Family Medicine, where midlife women are evaluated for menopause and sexual health-related concerns. All the women seen in these areas will complete multiple questionnaires as part of their clinical evaluation, including the PSQI. They also complete questionnaires assessing mood (Patient Health Questionnaire 9, PHQ-9), anxiety (Generalized Anxiety Disorder 7, GAD-7), and sexual function (Female Sexual Function Index, FSFI and the Female Sexual Distress Score-Revised, FSDS-R), Quality of Life-LASA), Perceived Stress Scale (PSS) and Resilience- (CD-RS10).

Review of medical records, images, specimens

- The study involves data that exist at the time of IRB submission and data that will be generated after IRB submission. Include this activity in the Methods section.

Data Analysis**Data Analysis Plan:**

Demographic characteristics are described using mean and standard deviations or frequencies and percentages based on the type of variable. For the primary aims being the feasibility and efficacy of the MUSE device, descriptive statistics and graphical displays will be presented for data obtained on frequency and duration of use over the treatment time of six months. A linear mixed model with repeated measures for each time point that

stress and sleep were taken. That information will be utilized to estimate the association between the average of time spent using the Muse-S with the stress and sleep level outcome. As secondary aim, the results of questionnaires for stress levels, mood and sexual function will be analyzed using the same linear mixed model with questionnaires being done at different intervals of the study to determine changes over time. Given the number of outcomes assessed, all analyses will be considered exploratory.

Endpoints:Primary Hypothesis:

- The regular use of the Muse headband will increase quality and quantity of sleep.

Secondary Hypothesis:

- The regular use of the Muse headband will decrease perceived stress levels, decrease anxiety, and improve sexual health.

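### A woman who reports suicidal ideation on a remote PHQ-9 and cannot be reached has no written next step, at 3 months or, if she completes the form by email, at 6 months

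*Combined protocol and SAP*

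**What the plan says.** All references are to the Combined protocol and SAP.

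**3 months (Study Follow-Up Visit).** There is no live contact at this visit: "3 month (questionnaire only visit): questionnaires will be sent via email". The coordinator looks at the PHQ-9 on the day it is completed. Then: "The coordinator will immediately notify the investigators if the score is severe or subject indicates suicidal ideation". Next: "The investigators will contact the patient immediately (same day) and if there is concern for active suicidal thoughts", they advise her to seek emergency evaluation, or "contact local authorities for a welfare check if the patient declines". If she is severely depressed without active thoughts or a plan, they point her to primary care, employee assistance or a therapist directory.

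**6 months (Study Follow-Up Visit).** Local women attend on site. For the rest ("Participants that are not local or cannot make an on-site visit"), the questionnaires go out by email and a phone visit is scheduled. On timing, the note says: "The PHQ 9 questionnaire will be reviewed at the time of the visit". If the score is 20 to 27 or ideation is indicated, the investigators are told and speak with her. If active thoughts are a concern, the investigator starts emergency evaluation at once.

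**Late questionnaires (Treatment phase).** For the 90-day questionnaires: "If not completed in a timely manner there will be reminders by email and/or phone to complete".

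**Entry (Exclusion Criteria).** One exclusion is: "A known, active, untreated clinically significant psychiatric condition".

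**The concern.** A screening item for suicidal ideation on a remotely completed form creates one foreseeable difficulty: the answer arrives and the woman does not respond. The protocol goes further than many in accepting that local authorities may be involved without her agreement, but it ties that step to refusal. A woman who refuses has at least been spoken to, assessed and advised. A woman who is never reached has had none of these, yet the text prompts no further action for her.

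The protocol does foresee non-response elsewhere: it provides reminders for an overdue form. It has no counterpart for a safety contact that fails.

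What is at stake is participant safety. No endpoint, estimate or analysis depends on it.

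**Working it through.** No figure in the plan bears on this, so the check is a reading of the two follow-up notes side by side, plus a search of the rest of the document for any provision covering a participant who cannot be reached. None was found.

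| Situation | 3 months (all by email) | 6 months (women completing by email) |
|---|---|---|
| When the PHQ-9 is looked at | Day of completion, by the coordinator | During the phone visit |
| Ideation indicated: first duty | Investigators make contact the same day | Investigators are notified and talk with her |
| Reached, active thoughts a concern | Emergency evaluation is recommended to her | Investigator starts emergency evaluation |
| Reached, and she refuses | Welfare check | Not separately stated |
| Reached, severely depressed, no active thoughts or plan | Primary care, employee assistance or directory | Same |
| **Not reached** | **Nothing written once attempts have failed** | **Nothing written; the form may not have been looked at** |

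**Step 1: 3 months.** The welfare-check condition follows directly on a recommendation made to the woman. She can decline only something that has been put to her, so the ordinary meaning of the trigger requires contact. Whether active thoughts are a concern is also, in practice, settled in conversation. If she is not reached, none of the written responses is triggered.

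**Step 2: 6 months.** The same-day check appears only in the 3-month note. The 6-month note has its own timing rule, which places review at the visit. The text does not say whether the emailed form is completed before, during or after the phone call. If it is completed beforehand and she then misses the call, the form has not been reviewed under the written procedure and no step follows. If it is completed after the call, review at the visit is not possible. The gap does not arise for women seen on site.

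**Step 3: exposure.** Target accrual is 50 (Subject Information).
- 3 months: 50 women × 1 emailed PHQ-9 = at most 50 forms; fewer if women drop out.
- 6 months: at most 50 forms, of which only those sent by email count. The documents give no split between on-site and remote women.
- Ceiling over both visits: 50 + 50 = 100 forms, reached only if everyone completes both and no one attends on site at 6 months.

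The number who would both indicate ideation and be unreachable needs two rates that the documents do not give, so none is calculated.

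**The case against.** **The duty is to make contact, which implies trying again.** This stands. A reader might infer that the protocol allows one call and then stops. The text does not support that: it requires same-day contact, names no mode, and an unanswered attempt does not discharge the duty. Repeat attempts that day are the natural reading. What remains is narrower: no step is written once those attempts have failed.

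**Clinical judgement covers it.** In part. Nothing forbids an investigator from requesting a welfare check for a woman who does not respond, and a reader should not infer that she would in fact be abandoned. But the note exists to direct staff at exactly this moment, and people hesitate to call in authorities outside the written condition.

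**A welfare check on the form answer alone would be too blunt.** This also stands. The protocol separates ideation indicated on a form, which triggers contact, from a judgement that active thoughts are a concern, which triggers emergency steps. An automatic same-day rule would skip that judgement. It would also work badly for a form submitted late in the evening. The remedy should therefore go through an investigator decision.

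**The 6-month visit is live, so the problem is confined to 3 months.** This is tempting, since a phone visit is live contact, but it holds only for women who take the call.

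**Contact details may be held elsewhere.** Fair. Consent and contact pages are not in the copy reviewed, so it cannot be said that phone numbers, locations or emergency contacts are missing. The existing welfare-check provision presupposes that a woman can be located. Holding the details would still not supply the missing instruction.

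**The event is rare.** Probably. Known, untreated psychiatric illness is excluded at entry, and a woman flagged at 3 months has used an electronic device that same day. The exclusion does not rule out ideation that arises later.

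**Conclusion.** The point holds as a gap in the safety procedure at both follow-up times. At 3 months there is no written step after same-day contact attempts fail, because the welfare check depends on refusal. At 6 months a woman who returns the form by email and misses the phone visit is, on the text, neither reviewed nor escalated.

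The surrounding procedure is otherwise sound: same-day review and contact at 3 months, and live review with mandatory emergency evaluation at 6 months. This is one missing branch in it.

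The conclusion rests on two readings: that the refusal condition carries its ordinary meaning, and that the 3-month same-day check does not extend to the 6-month visit, which has its own rule. It also assumes that no separate procedure outside the reviewed pages covers the case. The number of women affected cannot be estimated and is probably small. Because the consequence for one woman could be grave and the remedy is cheap, the change is worth considering. It does not touch the scientific results.

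**What to change.** 1. **3-month note.** Add that, when suicidal ideation has been indicated and a stated number of contact attempts within a stated number of hours have failed, the investigator must decide on escalation. The default is a welfare check, unless a reason against it is documented. The sponsor should set both numbers; counting in hours avoids the late-evening problem of a calendar-day limit.
2. **6-month note.** Require emailed PHQ-9 forms to be checked on the day of completion, as at 3 months, and apply the same rule if the woman cannot be reached or misses the phone visit.
3. **Contact details.** Confirm that a current phone number and location are available for each woman, since some are not local. If location is not already recorded, collect it.

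The cost is a few sentences in a protocol amendment, a small amount of coordinator time for the 6-month checks, and an occasional welfare check on a woman who turns out to be safe. The protocol already provides for contacting local authorities, so no new recipient of information is added. The consent wording could not be checked and should be read against the change. Endpoints, sample size and analysis stay as they are.

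### For local women the 3- versus 6-month comparison coincides with a move from emailed questionnaires to a coordinator visit, and nothing in the design or model separates the two.

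*Combined protocol and SAP*

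**What the plan says.** - **Baseline** (Consent and Screening). The coordinator meets the woman, obtains consent and screens her. Then: "They will be asked to complete the study questionnaires". Neither place nor mode is given. The paragraph after the exclusion criteria adds that women in these clinics already fill in most of the same scales as part of clinical care, but not whether those forms serve as baseline.
- **3 months, all women** (Treatment phase; Study Follow-Up Visit). "Participants will receive an email link at 90 days from REDCap to complete their questionnaires for the study", and "3 month (questionnaire only visit): questionnaires will be sent via email".
- **6 months, local women** (Study Follow-Up Visit). The plan describes "a study coordinator visit at Menopause and Women's Sexual Health Center for a final weight, body mass index, blood pressure check and questionnaires for local" women. Also: "The PHQ 9 questionnaire will be reviewed at the time of the visit".
- **6 months, other women** (same paragraph). "Participants that are not local or cannot make an on-site visit, questionnaires will be sent by email to be completed"; the coordinator also schedules a call with them.
- **Data capture** (Methods). "The data will be recorded in REDCap at baseline, 3 months, and 6 months".
- **Aim 2** seeks "to ascertain whether duration of treatment impacts efficacy".
- **Design and analysis** (Subject population; Data Analysis Plan). The trial is open label and single arm, with 50 women. A linear mixed model over the time points assesses change. No term for setting or mode is named, and all analyses are exploratory.

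**The concern.** The hypothesised outcomes (sleep, stress, anxiety, sexual health) are measured by questionnaire in women who know that they are using the device. Some scales are sensitive: the FSFI, the FSDS-R and the PHQ-9. Answers to such scales may differ between an emailed form and a clinic visit with study staff present, where one of the forms is reviewed on the spot.

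If they do differ, the model's change from month 3 to month 6 contains that difference for every woman who moved from email to clinic. In a two-arm trial with the same schedule in both arms, a common shift would cancel. Here nothing cancels it, and a reader looking at month 3 against month 6 to judge whether longer use helps could not tell it from a duration effect.

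**Working it through.** The plan states no figure on this point, so there is nothing to reproduce. The check has three steps.

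**1. Settings side by side**

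| Time point | Local women | Not local or unable to attend |
|---|---|---|
| Baseline | not stated; after coordinator meeting | not stated; after coordinator meeting |
| 3 months | emailed link | emailed link |
| 6 months | on-site coordinator visit | email, plus coordinator phone visit |

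For local women, time point and setting change together between months 3 and 6. For the others the mode stays the same, but a phone visit is added that month 3 did not have. Whether that call comes before or after the form is not stated.

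**2. Which contrasts carry a shift**

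Let *d* be the mean difference in score between on-site and emailed completion (unknown, either sign) and *p* the share seen on site at 6 months (unknown). Assume that a baseline completed at the coordinator meeting carries the same *d*, and ignore the phone visit. The artefact in each mean change is then:

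| Scenario | 0 to 3 months | 3 to 6 months | 0 to 6 months |
|---|---|---|---|
| As planned, baseline at the meeting | −d | +pd | −(1−p)d |
| As planned, baseline remote | 0 | +pd | +pd |
| Only the 6-month mode changed, baseline at the meeting | −d | 0 | −d |
| Same remote link at all three | 0 | 0 | 0 |

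The 3-to-6-month artefact is *pd* whatever the baseline mode. Changing month 6 alone removes it but, if baseline is completed at the meeting, enlarges the baseline-to-6-month artefact from (1−p)d to d in size. Only the last row is clean throughout.

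**3. How large *pd* could be**

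Assumptions: 50 women with complete data, no true 3-to-6-month change, within-woman correlation ρ of 0.5 or 0.7, and a two-sided 5% normal test. The documents give only the 50.

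SE of the mean paired change, in SD units = √(2(1−ρ)/50):
- ρ = 0.5: √(1.0/50) = 0.141
- ρ = 0.7: √(0.6/50) = 0.110

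Rejection rate = 1 − Φ(1.96 − pd/SE) + Φ(−1.96 − pd/SE).

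| p | d (SD) | pd (SD) | pd/SE, ρ 0.5 / 0.7 | Rejection rate, ρ 0.5 / 0.7 |
|---|---|---|---|---|
| 0.25 | 0.1 | 0.025 | 0.18 / 0.23 | 5.4% / 5.6% |
| 0.5 | 0.2 | 0.10 | 0.71 / 0.91 | 10.9% / 15.0% |
| 1.0 | 0.3 | 0.30 | 2.12 / 2.74 | 56.4% / 78.2% |

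The rates are the same if *d* is negative, and the rate is 5% if *d* is zero. In PSQI points (scale 0 to 21), assuming 40% to 80% on site and a shift of 0.25 to 1.0 points in either direction, *pd* runs from 0.4 × 0.25 = 0.10 to 0.8 × 1.0 = 0.80. That range does not transfer to the other scales.

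**The case against.** The strongest counter-argument concerns baseline. The only context described for it is a coordinator encounter. If the forms are completed there, the on-site 6-month visit matches baseline for local women and month 3 is the odd point; emailing everyone at month 6 would then damage the full-treatment contrast. This stands against changing month 6 alone, as the second table shows. It does not stand against aligning all three time points.

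Several stronger readings are tempting and are not supported:
- *Women answer alone at 3 months and under supervision at 6.* A reader might infer this, but no text says that emailed forms are completed alone or that the coordinator administers or watches the on-site forms. A local woman may self-complete in REDCap in private. What is documented is a change of setting and staff presence.
- *The shift flatters the device.* This is plausible when women answer at the clinic of the team that supplied it, but nothing in the documents fixes its direction or size.
- *This is the trial's only comparison of time on treatment.* The Data Analysis Plan also relates average time of use to outcome, and no 3- versus 6-month test is specified. Moreover, Methods gives six months of use while Treatment phase places the intervention portion in the first three. Those statements must be reconciled before months 3 to 6 can be read as time on treatment.
- *Local and remote women will appear to differ.* No such analysis is planned, and remote women have a phone visit of their own at month 6.

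It is also fair that the missing control arm limits causal reading more than place of completion does, and that all analyses are exploratory. That lowers the weight of the point. It does not remove the bias from the estimate.

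**Conclusion.** The point holds as a limit on interpretation. For women seen on site at 6 months, the 3-to-6-month change cannot be separated from a change of setting and staff presence, because there is no control arm and the plan neither names a setting term nor says that the setting will be recorded. The change bears on Aim 2.

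The size is *pd*, and the documents give neither factor. Under the assumed values it runs from negligible (0.025 SD) to dominant (0.30 SD, if every woman is seen on site and the shift is 0.3 SD). The finding rests on the mismatch of settings, which is documented, and not on any of these values. It does not show that a benefit is exaggerated, and it does not overturn a confirmatory result, since none is planned. The change is worth making because it costs little and because a setting that goes unrecorded may not be recoverable later.

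**What to change.** 1. **One mode at all three time points.** Send every woman the same REDCap self-completion link at baseline, 3 months and 6 months. At follow-up she completes it before any coordinator contact, on site or by phone, with on-site completion only as a fallback if the form has not been done. Keep the 6-month visit for weight, BMI and blood pressure.
2. **Do not change month 6 without baseline.** State the baseline mode explicitly, and whether forms filled in for clinical care count as baseline.
3. **Record the completion setting** (emailed or on site, before or after coordinator contact) for each form at each time point.
4. **Add a sensitivity analysis** to the Data Analysis Plan: either a setting term in the mixed model or a repeat of the 3-to-6-month estimate in women who completed remotely at both follow-ups. Both are weaker than step 1. A setting term relies on local and non-local women having the same true change, and cannot be separated from time if all attend on site. The restricted analysis is small: with half on site it has 25 women, and at ρ = 0.5 the SE rises from 0.141 to √(1.0/25) = 0.200 SD.

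**Cost.** Protocol wording and one REDCap field. The link and reminders already exist for 3 months, and email is already used for remote women at 6 months. Some local women will need reminders or may complete late. The sponsor must reconcile the PHQ-9 review wording in the 3-month and 6-month paragraphs with the new timing; how that review is done is for the investigators.
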